2.0 Background

2.1 Significance of Research Question/Purpose:

Rigorous prior research in small-scale human studies show promising effects of TRE. In contrast to intentional caloric restriction, TRE presents a simplified

MEDICAL PROTOCOL (HRP-590)

PROTOCOL TITLE: Piloting a Family-Based Intervention of Time-Restricted Eating to Treat Obesity

VERSION DATE: 07Sep2022

approach to obesity treatment. TRE establishes a consistent daily eating window (~8-12 hours) with *ad libitum* intake, while preserving a daily 12-16 hour fasting period. Our preliminary data in adults (PI: [name]), show that 12 weeks of TRE with *ad libitum* intake in adults who are overweight results in reduction of weight (-3.7%), fat mass (-4%) and visceral fat (-11.1%).¹ Moreover, our preliminary data show that TRE improves quality of life relative to baseline or unrestricted eating.²

TRE's agnostic approach to diet allows participants to eat *ad libitum* during their eating window according to food availability and cultural food preferences. Consequently, TRE presents a practical means of implementing prolonged fasting in adults, reducing eating occasions by 22%¹ and daily caloric intake by ~8-20%.^{3,4} TRE can be administered remotely, reducing frequently cited barriers to intentional caloric restriction such as transportation, scheduling or financial barriers.^{5,6} TRE requires less staff time, as our preliminary data show that the average visit duration for monitoring intentional caloric restriction in adults was 46.1 (33.7) [mean (SD)] minutes, whereas the duration for TRE was significantly lower ($p<0.01$) at 24.4 (7.7) minutes.² In summary, TRE's simple approach of restricting the eating window results in weight reduction and increased quality of life while taking less staff and participant time than traditional obesity treatment approaches, likely increasing acceptability of TRE.

It is well documented that obesity clusters in families. As such, obesity treatment should be made available to both children and adults, simultaneously.

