Traditionally, family-based therapy has been implemented by a few research groups and is time and resource intensive.^{7,8} Even on an individual level, multiple barriers likely impede the implementation and effectiveness of, as well as adherence to intentional caloric restriction. In contrast, TRE's simple approach presents a potentially viable alternative to intentional caloric restriction. By allowing *ad libitum* intake during the eating window, TRE mitigates the understanding, literacy, dietary, and numeracy barriers often arising from intentional caloric restriction.⁵ Furthermore, the contact hours necessary to implement TRE will be significantly less than other interventions. This study will provide preliminary data to demonstrate feasibility and acceptability of TRE in the family unit, providing critical preliminary data to support NIH-level funding for a more detailed analysis of TRE in families.

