3.0 Study Endpoints/Events/Outcomes

- 3.1 Primary Endpoint/Event/Outcome: Evaluate feasibility and acceptability of implementing TRE in families by quantifying recruitment, adherence and intervention burden. We anticipate that we will recruit ~3 families per month for a total of 10 families in each intervention group (N=20), with a retention rate of 70-80% across both groups.

MEDICAL PROTOCOL (HRP-590)

PROTOCOL TITLE: Piloting a Family-Based Intervention of Time-Restricted Eating to Treat Obesity

VERSION DATE: 07Sep2022

- In the TRE group, there will be close agreement between tooth brushing times (recorded with Bluetooth-enabled toothbrush) and self-reported eating window.
- Family-based TRE will result in less intervention burden than intentional caloric restriction, as documented by less staff time administering the intervention.

[figure not shown]
3.2 Secondary Endpoint(s)/Event(s)/Outcome(s):

- Compare weight/BMI change between the TRE group and the SOC group. We hypothesize that the weight/BMI outcomes between the two groups will be comparable.
- Assess relationship between child and adult weight/BMI outcomes with TRE. We hypothesize that parent and child weight/BMI change will be positively correlated.

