8.2 Exclusion Criteria

- Concurrent participation in another weight loss study
- Taking any medications for weight loss
- Pregnancy or anticipation of pregnancy in next 6 months (for the parent)
- 3+ on Eating Disorder Survey (see attached)
- Must be on a stable dose of any weight-altering medications

8.3 Prescreening/Consent: Individuals who appear to meet the study criteria based on a pre-screening telephone call will be asked to participate in a virtual (video) visit. At that visit, consent will be discussed and obtained, height and weight will be self-reported by parent for both parent and child, so that estimated BMI can be calculated, and inclusion/exclusion criteria will be reviewed. Individuals who meet the BMI requirement and the inclusion/exclusion criteria will enroll in the study.

Following consent and prior to the Baseline/Week 0 session, parents will be

MEDICAL PROTOCOL (HRP-590)

PROTOCOL TITLE: Piloting a Family-Based Intervention of Time-Restricted Eating to Treat Obesity

VERSION DATE: 07Sep2022

contacted by the University of Minnesota Nutrition Coordinating Center (NCC) staff and will be asked to provide three 24-hour dietary recalls for themselves and for their child (for a total of six). NCC staff will be blinded to participant intervention assignment. Using this 24-hour dietary recall data, we will calculate the daily average caloric intake and healthy eating index, as well as the eating window.

Baseline/Week 0: Individuals will be asked to come to the Delaware Clinical Research Unit (DCRU). At that visit, height and weight will be measured so that BMI can be calculated. Individuals who no longer meet inclusion/exclusion criteria will be excluded (e.g., outside BMI range based on in-person measurement compared to self-reported). Participants who meet the inclusion/exclusion criteria will be randomized to their intervention group. Participants will be provided with a Bluetooth-enabled scale and instructed to weigh themselves once per week. Participants will also be provided with Bluetooth-enabled toothbrushes. Participants randomized to the TRE treatment will be asked to brush their teeth twice daily and to brush their teeth within 30 minutes after the evening meal to note that they have ceased eating until the next day.

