Participants randomized to SOC will have a dietary session with a dietitian to discuss food portions and food selections that encourage reduced caloric intake. They will be given portioned dishes as part of this treatment. Participants randomized to TRE will meet with the dietitian to discuss the length and timing of the eating window. All parents will be asked to complete demographic information and questionnaires. Parents will be told that they will receive periodic emails (see schedule of events) asking them to log into REDCap and complete a survey about what time the family started and stopped eating meals for the day.

Weeks 1, Week 2, Week 3, Week 4, Week 6, Week 8, Week 10: Parents will have a dietary session with the dietitian to discuss their respective intervention. That is, parents in TRE will discuss implementation of the eating window and parents in SOC will discuss food portions and food selections that encourage reduced caloric intake. Parents will be reminded that they should utilize the Bluetooth-enabled scale to weigh themselves as well as their child once per week. Parents will be reminded to fill out the REDCap survey daily and will be reminded to utilize the Bluetooth-toothbrush.

Week 12: Participants will return to the Delaware Clinical Research Unit. They will receive a session with the study dietitian. The height and weight of the parent and the child will be measured and BMI calculated. The parent will be asked to fill out questionnaires about eating as well as a satisfaction survey.

MEDICAL PROTOCOL (HRP-590)

PROTOCOL TITLE: Piloting a Family-Based Intervention of Time-Restricted Eating to Treat Obesity

VERSION DATE: 07Sep2022

Parents will be contacted by a Registered Dietician from the University of Minnesota Nutrition Coordinating Center (NCC) staff and will be asked to provide three 24-hour dietary recalls for themselves and for their child (for a total of six).

Follow-up: The parent will receive a satisfaction survey to be completed electronically at 1, 3, and 6 months following treatment .

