12.0 Withdrawal of Participants

12.1 Withdrawal Circumstances: Individuals are free to withdraw from study participation at any time, they should just inform the study team.

12.2 Termination Procedures: Data that had been collected before the dyad elected to withdraw from the study will be kept in the participant file. No additional information will be collected from the dyad after they have indicated that they no longer want to participate in the study.

MEDICAL PROTOCOL (HRP-590)

PROTOCOL TITLE: Piloting a Family-Based Intervention of Time-Restricted Eating to Treat Obesity

VERSION DATE: 07Sep2022

12.3

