15.0 Statistical Considerations

Analysis Plan: We will summarize feasibility and adherence measures (recruitment and retention rate, proportion of days with documented eating window, eating window length) using sample proportions, means (standard deviations), and medians (interquartile ranges). Proportion of families completing the study (retention rate) will be compared between intervention groups using Fisher's exact tests. Agreement between toothbrush reported eating window and survey reported eating window will be evaluated using mixed effects models¹⁶ (to account for repeated measures for each family) and Bland-Altman Plots.¹⁷

The primary outcome analysis will use a linear GEE model, with independence working correlation for family units, to compare change in BMI during the 12-week period (pre-post) between participants assigned to the TRE intervention compared to the standard of care. This model will allow for estimating the TRE effect for children and adults while accounting for the correlation between parent and child measures. If we do not detect a difference in TRE effect for children and adults ($p\text{-value} \geq 0.1$) the treatment assignment by child indicator interaction will be removed from the model. A similar approach will be used to compare changes in measures of diet quality (average caloric intake and HEI), eating and feeding behaviors, appetite, and quality of life measures between groups. Generalized linear mixed effects models will be used to evaluate

MEDICAL PROTOCOL (HRP-590)

PROTOCOL TITLE: Piloting a Family-Based Intervention of Time-Restricted Eating to Treat Obesity

VERSION DATE: 07Sep2022

differences in weight trajectory between intervention groups. We will evaluate the correlation between parent and child change in BMI during the study using Pearson's correlation coefficient, or Spearman's correlation coefficient (if data visualizations indicate a non-linear trend). Total intervention time (sum of session time across the study) will be compared between groups using t-tests (or Wilcoxon rank sum tests if measures are highly skewed).

We will check data distributions before conducting statistical tests and will transform the data if the normality assumption is not met. Logistic regression models will be used in place of linear regression models for binary data, as appropriate. Analyses will be performed in R or SAS (Version 9.4, SAS Institute Inc., Cary, NC)

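### Staff time is compared only as a study total, which mixes session length with attendance; adding minutes per attended session would be a cheap improvement

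*Combined protocol and SAP*

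**What the plan says.** Section 3.1 places intervention burden under the primary endpoint, with this hypothesis: "Family-based TRE will result in less intervention burden than intentional caloric restriction, as documented by less staff time administering the intervention". The only analysis is in Section 15.0: "Total intervention time (sum of session time across the study) will be compared between groups using t-tests (or Wilcoxon rank sum tests". No comparison of time per session is planned.

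The two arms have the same contact schedule. Section 8.3 says of the interim visits, for both arms: "Parents will have a dietary session with the dietitian to discuss their respective intervention". The Schedule of Events adds a session at baseline and one at week 12.

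On attrition, Section 3.1 anticipates 20 families "with a retention rate of 70-80% across both groups". Section 12.2 adds: "Data that had been collected before the dyad elected to withdraw from the study will be kept in the participant file". Nothing is collected after withdrawal. Section 15.0 compares the proportion of families completing between arms, but does not mention the number of sessions attended.

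The evidence behind the hypothesis, in Section 2.1, is expressed per visit: "the average visit duration for monitoring intentional caloric restriction in adults was 46.1 (33.7) [mean (SD)] minutes", against 24.4 (7.7) minutes for TRE. The same section also argues in terms of totals: "the contact hours necessary to implement TRE will be significantly less than other interventions".

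**The concern.** The number of planned sessions is equal by design, so delivered time can differ between arms only through session length or attendance. The rationale concerns session length. The planned test adds the two together.

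A family that leaves early has a small total and looks like a low-burden family. A lower TRE total could therefore mean shorter sessions, more families leaving, or both, and the planned output would not say which. The comparison of completion by arm helps only partly, because it does not show when the leavers left.

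Section 15.0 says the pilot exists to supply feasibility and variability figures for a full trial. Planning that trial needs session length and attendance as separate quantities, each with its own spread.

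**Working it through.** **Inputs from the documents.** Ten families per arm and alpha 0.05 (Section 15.0, taken as two-sided); retention 70-80% (Section 3.1); minutes per visit 24.4 (SD 7.7) for TRE and 46.1 (SD 33.7) for caloric restriction (Section 2.1).

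**Assumptions not in the documents.** Session times are normal. The correlation of session length within a family is ρ = 0.5. A family that leaves has attended 1 to 8 sessions with equal probability, mean 4.5. Its partial sum enters the test.

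**Plan's own figures.** The schedule gives sessions at baseline, weeks 1, 2, 3, 4, 6, 8, 10 and week 12, which is nine. The payments in Section 11.3 agree: 2 × 35 + 7 × 15 = 175 dollars. The only power figure concerns BMI change. With effective n per group 20/1.1 = 18.18 and 20/1.8 = 11.11, a noncentral t calculation gives 0.956 and 1.249, matching the stated 0.96 to 1.25. There is no power figure for staff time to reproduce.

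**Expected totals.** With retention r, mean sessions attended are E(K) = 9r + 4.5(1 − r).
- Full retention: 9 × 24.4 = 219.6 and 9 × 46.1 = 414.9 minutes, a difference of 195.3.
- 80% in both arms: E(K) = 8.10; 8.10 × 21.7 = 175.8 minutes.
- 70% in both arms: E(K) = 7.65; 7.65 × 21.7 = 166.0 minutes.
- TRE 80%, control 70%: 7.65 × 46.1 − 8.10 × 24.4 = 155.0 minutes.
- TRE 70%, control 80%: 8.10 × 46.1 − 7.65 × 24.4 = 186.8 minutes.

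A control family needs 219.6/46.1 = 4.76 average sessions to match a TRE completer, so one that stops after four counts as less burdensome.

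**Spread of the total.** For per-session mean μ and SD s,

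Var(total) = s²[ρE(K²) + (1 − ρ)E(K)] + μ²Var(K).

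At 80%, E(K²) = 0.8 × 81 + 0.2 × 25.5 = 69.9 and Var(K) = 69.9 − 8.10² = 4.29. For TRE this gives 59.29 × (34.95 + 4.05) + 595.36 × 4.29 = 2,312 + 2,554 = 4,866, so the SD is 69.8 minutes and 52.5% of the variance is attendance. The TRE SD is 51.7 at full retention and 74.9 at 70% (61.9% attendance). The control SD barely moves: 226.1, 231.1 and 230.8.

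**Power by simulation** (20,000 trials; 1,500 to 4,000 for the mixed model), same retention in both arms:

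| Analysis | 100% | 80% | 70% |
|---|---|---|---|
| Total, t-test | 71% | 58% | 53% |
| Mean minutes per attended session, t-test | 71% | 69% | 68% |
| Total, Welch | 67% | 54% | 49% |
| Mean minutes per attended session, Welch | 67% | 65% | 64% |
| Mixed model on session minutes, variances by arm | 66% | 66% | 64% |

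The levels depend on the assumptions. At 80% retention, total against per-session mean (t-test) is 79% against 90% with ρ = 0.2, 46% against 55% with ρ = 0.8, and 63% against 77% with gamma session times and ρ = 0.5. The per-session advantage appears in each case.

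**False positives when true session lengths are equal** (35 minutes, SD 11.3 in both arms). At 70% against 80% retention the expected total is 1 − 7.65/8.10 = 5.6% lower in the arm losing more families. The t-test on the total rejects in 6.2% of trials. At 60% against 90% it rejects in 16.5%. The mixed model gives 4.6% and 4.8%.

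**Reversal.** With the Section 2.1 durations, the TRE mean total exceeds the control mean total in 0.8% to 1.9% of trials across the 70-80% patterns.

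**The case against.** The hypothesis is about staff time for the intervention, and summed session time measures exactly that. Counting every delivered minute, including those of families that later left, is also the natural reading of Sections 12.2 and 15.0 together. This stands: the total is not a wrong endpoint, and a sentence fixing its definition only removes doubt.

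Power is a limited argument. The plan claims none for staff time, the total and the per-session mean are different quantities, and the levels rest on assumed correlation, dropout and distribution. A normal distribution with mean 46.1 and SD 33.7 even makes about 8.6% of control sessions negative in length. This also stands, so the percentages should be read as a pattern rather than a forecast.

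A reader might infer that dropout could produce a false claim for TRE or reverse the result. The documents do not support that. Within the anticipated retention the error rate is close to nominal and reversal is rare. The 16% figure needs a 60% against 90% split, outside the planned range, and a split that large would show in the planned comparison of completion.

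That comparison does not fully answer the point. With 7 of 10 completers, three leavers stopping after one session give 63 + 3 = 66 sessions delivered; stopping after eight they give 63 + 24 = 87. These are extremes, each with probability 1/512 under uniform dropout, but they show that completion does not determine attendance.

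**Conclusion.** The point holds as a cheap improvement. The plan's only staff-time comparison cannot separate session length from attendance, although the arms have identical schedules and 20-30% attrition is expected.

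Under the stated assumptions, the cost within the planned retention range is about 11 to 15 percentage points of power relative to the per-session mean (58% against 69% at 80%; 53% against 68% at 70%). In addition, more than half the variance of the TRE total reflects attendance. The false-positive rate is only about 6%, and the direction reverses in at most 2% of trials. Error becomes material, about 16%, only at an imbalance such as 60% against 90%.

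Two stronger readings go too far. One is that the total is invalid or should be replaced: it still answers how much staff time was spent. The other is that any staff-time conclusion must rest on the per-session result alone: Section 3.1 makes a claim about the intervention as a whole. The per-session result is needed only to attribute a lower total to shorter sessions.

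**What to change.** In Section 15.0:

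1. Keep total intervention time, and state that it counts all minutes delivered to every randomised family, whether or not the family completed.
2. Add a between-arm comparison of minutes per attended session: a mixed model with arm and session number as fixed effects, a family random intercept and variances allowed to differ by arm, reported as a difference with 95% CI.
3. Report sessions attended by arm.
4. State that a lower TRE total will be attributed to shorter sessions only if the per-session comparison supports it.

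A Welch test on each family's mean minutes is an acceptable simple version only if session length does not change with session number; otherwise early leavers shift their arm's mean. For example, with an assumed 30 extra minutes at the first session, equal arms, early dropout and 60% against 90% retention, its error rate is 10-12%. At 70% against 80% it stays near 5%.

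The cost is a few sentences and one extra model on session times that must be recorded anyway to form the sum. Families that start are not lost, because randomisation and the first dietitian session are both at the Baseline/Week 0 visit (Section 8.3: "Participants who meet the inclusion/exclusion criteria will be randomized to their intervention group"). The downside is that the per-session estimate is conditional on attendance, so it must be read beside the attendance figures.

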	Prescreening/Consent	Baseline / Week 0	Week 1	Week 2	Week 3	Week 4	Week 5	Week 6	Week 7	Week 8	Week 9	Week 10	Week 11	Week 12	Follow-Up Month 1	Follow-Up Month 3	Follow-Up Month 6
Consent	V																
Dietary treatment session		P	V	V	V	V		V		V		V		P			
Demographics		P															
Height and weight		P												P			
Weight via Bluetooth-scale		X	X	X	X	X	X	X	X	X	X	X	X	X			
Questionnaires																	
• Child Eating Behavior Questionnaire		P/V															
• Adult Eating Behavior Questionnaire																	
• Child Feeding Questionnaire																	
• Peds-QL																	
• Peds-QL Parent Report Versions (aged 2-4, 5-7 or 8-12)															P/V		
• Peds-QL Adult Quality of Life Inventory Questionnaire																	
24-hour recall		V													V		
Satisfaction survey															X	X	X
Daily time log ¹			← to be done via REDCap for 5 consecutive days three times during treatment (e.g., weeks 1, 6 and 12)→														
Use of Bluetooth-toothbrush			← to be done twice daily at home by participants→														

Note: P= in person, V= via virtual visit, X=completion time

¹ All families will receive automated, email-based REDCap survey for the parent to document the time that they and their child started eating in the morning and their last eating occasion of the day. This will serve as a measure of the length of the eating window.

MEDICAL PROTOCOL (HRP-590)

PROTOCOL TITLE: Piloting a Family-Based Intervention of Time-Restricted Eating to Treat Obesity

VERSION DATE: 07Sep2022

5.2 Study Duration:

- It is anticipated that it will take six months to recruit the 20 parent/child dyads (40 individuals total) to participate in the study.
- Each dyad will be enrolled in the study for 12-14 weeks for screening through treatment. Follow up surveys will be sent at 1, 3, and 6 months following the end of treatment.

5.3 Use of radiation: Not applicable.

5.4 Use of Center for Magnetic Resonance Research: Not applicable.

6.0 Data and Specimen Banking: Not applicable.

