10.0 Local Number of Participants

10.1 Local Number of Participants to be Consented: A total of 20 parent/child dyads (40 total individuals) will be asked to participate in the study. 10 parent/child

MEDICAL PROTOCOL (HRP-590)

PROTOCOL TITLE: Piloting a Family-Based Intervention of Time-Restricted Eating to Treat Obesity

VERSION DATE: 07Sep2022

dyads will be randomized to standard care and 10 parent/child dyads will be randomized to time-restricted eating.

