Sample Size: Since the primary purpose of this pilot study is to collect preliminary data (specifically feasibility and variability measures) to inform study design for a fully powered clinical trial, this pilot study is powered to detect large differences in BMI change between groups. With n=20 per group (10 child-parent pairs), correlation between child-parent pairs ranging from 0.1 to 0.8, and an alpha= 0.05 significance level, we will have 80% power to detect a difference in BMI change (pre-post) between treatment groups of 0.96 to 1.25 standard deviations (Cohen's d of 0.96 to 1.25, a large effect size).

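### The stated 80% power for 0.96–1.25 SD needs all 20 dyads analysed; at the protocol's own 70–80% retention it is about 63–70% if dropouts have no Week 12 BMI

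*Combined protocol and SAP*

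**What the plan says.** The Sample Size paragraph of Section 15.0 takes 20 individuals (10 parent-child pairs) per group, a parent-child correlation of 0.1 to 0.8 and alpha 0.05, and concludes: "we will have 80% power to detect a difference in BMI change (pre-post) between treatment groups of 0.96 to 1.25 standard deviations".

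Those 10 pairs per group are everyone the protocol plans to recruit. Section 10.1 states: "A total of 20 parent/child dyads (40 total individuals) will be asked to participate in the study", split 10 and 10 between the arms. Sections 4.1 and 5.1 give the same total.

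Section 3.1 anticipates recruiting 10 families per group "with a retention rate of 70-80% across both groups".

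Four further places bear on who will have the outcome:

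- The Analysis Plan in Section 15.0 compares the pre-post change in BMI over 12 weeks between arms, and treats retention as the share of families that complete the study.
- Section 5.2 states: "Each dyad will be enrolled in the study for 12-14 weeks for screening through treatment". It describes the 1, 3 and 6 month surveys separately.
- The Week 12 paragraph of Section 8.3 places the closing measurement at the clinic visit: "The height and weight of the parent and the child will be measured and BMI calculated". The Schedule of Events lists measured height and weight only at baseline and Week 12.
- Section 12.2 ends data collection once a dyad says it no longer wants to take part.

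**The concern.** The power statement and the retention expectation are in the same protocol but are never connected. The first is worded as what the trial will have. The second says that 20–30% of the families behind it are expected to be lost. There is no allowance for dropout in the sample size, no replacement rule, and no missing-data method for BMI change.

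What is at stake is how the BMI result will be read. The declared primary endpoint is feasibility and acceptability, and nothing in the protocol turns on reaching 80% power, so the pilot itself is not undermined. But Section 15.0 labels the BMI model as its primary outcome analysis, and Section 3.2 hypothesises comparable results in the two groups. A non-significant comparison is therefore the expected outcome, and the stated detectable difference tells a reader in advance how large a difference the study could plausibly have missed. As written, that figure is too favourable.

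**Working it through.** **Inputs.** From Section 15.0: 10 dyads per arm, correlation ρ from 0.1 to 0.8, alpha 0.05, power 80%, difference d from 0.96 to 1.25 SD. From Section 3.1: retention 70–80%, so 0.7 × 10 = 7 to 0.8 × 10 = 8 dyads per arm if loss is equal. The sidedness of alpha is not stated, so I take two-sided. A one-sided normal approximation gives 0.83–1.06 SD and does not match the plan.

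**Method.** With m dyads per arm, each with two correlated members:

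- design effect = 1 + (2 − 1)ρ = 1 + ρ
- effective n per arm = 2m/(1 + ρ)
- standard error of the difference in SD units = √((1 + ρ)/m)
- degrees of freedom = 2 × effective n − 2
- power from the noncentral t distribution with noncentrality d/SE

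**Step 1: reproduce the plan (m = 10).**

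- ρ = 0.1: effective n = 20/1.1 = 18.18; SE = √(1.1/10) = 0.332; df = 34.4. Power at 0.96 SD is 80.3%; 80% power corresponds to 0.956 SD.
- ρ = 0.8: effective n = 20/1.8 = 11.11; SE = √(1.8/10) = 0.424; df = 20.2. Power at 1.25 SD is 80.1%; 80% power corresponds to 1.249 SD.

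Both ends of the stated range are recovered, with every recruited dyad in the analysis.

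**Step 2: same method, fewer dyads.** For example, with m = 8 and ρ = 0.1: effective n = 16/1.1 = 14.55; SE = √(1.1/8) = 0.371; noncentrality = 0.96/0.371 = 2.59; df = 27.1; power = 70.4%.

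| Dyads analysed per arm | Power at 0.96 SD (ρ = 0.1) | Power at 1.25 SD (ρ = 0.8) | Difference at 80% power (ρ = 0.1 to 0.8) |
|---|---|---|---|
| 10 | 80.3% | 80.1% | 0.96–1.25 SD |
| 9 | 75.8% | 75.3% | 1.01–1.33 SD |
| 8 | 70.4% | 69.6% | 1.08–1.42 SD |
| 7 | 64.1% | 62.9% | 1.16–1.53 SD |

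The chance of missing a true difference of the stated size is therefore 29.6–30.4% with 8 dyads per arm and 35.9–37.1% with 7, against the nominal 20%.

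**Step 3: sensitivity.**

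- Unequal loss with the same totals is slightly worse. With 9 and 7 dyads, power is 69.7% / 68.9% and 80% power needs 1.09–1.43 SD. With 8 and 6 dyads, power is 63.2% / 62.0% and 80% power needs 1.17–1.55 SD.
- At 7–8 dyads per arm, a normal approximation gives 68–75%, a t-test with degrees of freedom counted in dyads gives 61–69%, and one counted in individuals gives 65–72%. The exact figure depends on the method; every version is below 80%.

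**The case against.** The strongest reply is that nothing has been miscalculated. The sentence states its condition, 10 pairs per group, and under that condition the range is right. That is true: the fault lies in what the figure is made to represent, not in its derivation. But the condition equals the full recruitment target, the claim is worded as what the study will have, and the same protocol expects fewer families.

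Second, the 63–70% depends on reading retention as having a Week 12 BMI. Families lost only during the 1 to 6 month surveys would still have the outcome, and a family that skips sessions without withdrawing might still attend Week 12. This stands as a real uncertainty. Section 5.2 counts enrolment through treatment only, which favours the Week 12 reading but does not settle it. If 9 dyads per arm are measured, power is 75–76%, so the shortfall is smaller but remains.

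Third, the weekly Bluetooth weights might cover partial completers. The plan uses them in a separate trajectory model and does not say they would replace a missing Week 12 BMI. No home height measurement is scheduled, which matters in growing children.

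Fourth, the consequence is small. The study claims only to detect large differences, and that remains true. The spread from the unknown correlation is already 1.25 − 0.96 = 0.29 SD, while attrition moves the figure by 0.12–0.17 SD (8 per arm) or 0.20–0.28 SD (7 per arm). Once data exist, the confidence interval will be a better guide than any planned detectable difference. All of this stands and limits the importance of the point. It does not make the published figure right under the protocol's own expectation, and the attrition shift comes on top of the correlation spread.

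**Conclusion.** The concern holds. The 80% figure applies only if all 20 dyads are analysed. At the protocol's own 70–80% retention, the same method gives about 70% power with 8 dyads per arm and 63–64% with 7, and the differences detectable with 80% power rise to 1.08–1.42 SD and 1.16–1.53 SD.

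This rests on four assumptions: alpha is two-sided; whole dyads are lost; loss is roughly equal between arms; and retention refers to dyads with a Week 12 BMI. The last is the one the documents leave most open. Relaxing it to 9 dyads per arm gives 75–76% power and 1.01–1.33 SD. Unequal loss lowers power slightly further.

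This should be corrected, but it does not threaten the feasibility aims of the pilot.

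**What to change.** Restate the power sentence in Section 15.0 (Sample Size) so that it covers both cases, for example:

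> If all 10 dyads per group are analysed, 80% power corresponds to a difference in BMI change of 0.96 to 1.25 SD (parent-child correlation 0.1 to 0.8). At the expected 70–80% retention (14–16 dyads with a Week 12 BMI), it corresponds to about 1.08–1.42 SD with 8 dyads per group or 1.16–1.53 SD with 7.

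In the same place, say whether the 70–80% in Section 3.1 refers to attendance at the Week 12 visit or to completion of the later surveys.

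The cost is two sentences and a less favourable stated figure. It needs no extra families, visits or analyses; for a pilot with a feasibility endpoint, inflating enrolment is not necessary.
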